14. Diabetes by history, or as indicated by an abnormal hemoglobin A1c
15. Gastric bypass, metabolic disorders, or other conditions that affect adipokines
16. Abnormalities on screening laboratory tests (hemoglobin A1c, complete blood count, thyroid,

hepatic and renal function) including specifically a hemoglobin <12 g/dl (given multiple blood draws) judged by the investigator to be medically relevant

17. Hearing loss interfering with ability to respond to auditory stimuli
18. Cardiovascular illness
19. Neurological illness
20. Psychiatric illness, defined by clinical assessment at baseline as:
 - a. Current depression as indicated by an elevated score on the PHQ-8
 - b. A lifetime history of major depressive disorder, bipolar disorder, eating disorder, or psychotic symptoms
 - c. Current suicidal or homicidal ideation, or any prior suicide attempt or inpatient psychiatric hospitalization
21. Current medical or psychiatric conditions or medicine use judged by the investigator to interfere with study procedures or data collection
 - a. An alcohol or substance-use disorder active within the past year

B. Inclusion/Exclusion Criteria for Pilot Study Participants

Inclusion Criteria for Pilot Study Participants:

1. Healthy premenopausal women 21–45 years old
2. Habitually sleep 7–9 hours per night and usual bedtime before 12 midnight
3. No lifetime history of hot flashes
4. Body mass index <35 kg/m²
5. Good general health
6. Ability to understand and willingness to sign written informed consent document

Exclusion Criteria:

1. Current medical or psychiatric conditions or medicine use judged by the investigator to interfere with study procedures or data collection
2. Pregnancy
3. Breastfeeding
4. Regular tobacco use
5. Shift workers
6. Diagnosis of obstructive sleep apnea
7. Insomnia symptoms as indicated by a score on the Insomnia Severity Index suggesting subthreshold or clinically significant insomnia symptoms
8. Hearing loss interfering with ability to respond to auditory stimuli
9. Current depression, defined by a score >3 on the PHQ-2

Off-Study Criteria:

1. Emergence of significant psychiatric symptoms, suicidal or homicidal ideation
2. Development of any significant medical problem
3. Pregnancy
4. Significant deviations from study protocol, including enrollment in another research protocol that may influence the results of the current protocol.

Study Procedures Overview

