Briefly describe study procedures. Include any local site restrictions, for example, “Subjects enrolled at Partners will not participate in the pharmacokinetic portion of the study.” Describe study endpoints.

Screening Phase (1-2 months)

- **Telephone/Pre-screening:** Consent to screen will be obtained orally on the phone for the initial screening procedures and diaries. Women who verbally consent to screening and are interested in participating in this trial will answer some questions by phone to assess preliminary eligibility. The Berlin Questionnaire will be administered to screen for sleep apnea, and questions about general medical and mental health will be asked to screen for any major exclusion criteria. Those who are eligible and interested will be scheduled for an initial remote screening and research consent visit with a study clinician.
- **Screening visit 1a (remote):** Screening visit 1a will be conducted remotely. Written informed consent will be obtained via electronic signature using REDCap e-consent template and initial eligibility criteria will be assessed by a clinician, including a medical and psychiatric interview, and sleep interview. All women who sign the consent form will be assigned a study identification number regardless of eligibility status. Eligible participants will start monitoring their menstrual cycles and tracking their sleep after this visit.
- **Screening Visit 1b (in-person):** At this visit, a clinician will conduct a physical exam, and a blood draw will be taken for screening assays (e.g., CBC, glucose, insulin, HCG, TSH), for baseline levels of adipokines, metabolic and reproductive hormones, and for measures of immune function related to sleep and menopause. Once lab results are reviewed by a study clinician, final eligibility will be assessed. Eligible participants will be scheduled for Sleep Block 1, leuprolide injection, and dual-energy x-ray absorptiometry (DXA) scan.

Sleep Block 1 (10 days – two weeks before GnRH Agonist injection)

- Subjects will be admitted for two five night stays within the BWH Clinical And Translational Science Center/Center for Clinical Investigation (CCI) inpatient unit. Subjects will also complete at-home procedures, including an at-home PSG procedure. Subjects may log meals before inpatient admission and for up to 7 days after discharge with the app MealLogger™

GnRH Agonist Injection (1 day)

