- Subjects will come to one of the outpatient research units to be given an injection of leuprolide (GnRH agonist). The timing of ovulation will have been previously determined based on the collection of at least 3 menstrual cycle start dates. Leuprolide will be administered in the week prior to an expected menstrual cycle start date. If the subject starts her menstrual cycle early prior to receiving leuprolide, the protocol will be extended to the next cycle. On the day of the scheduled appointment for the injection, a urine pregnancy test will be performed to confirm that the subject is not pregnant and blood will be drawn to measure reproductive hormone levels.

Sleep Block 2 (10 days – 4 weeks after GnRH Agonist Injection)

- Subjects will be admitted for two five night stays within the BWH Clinical And Translational

Science Center/Center for Clinical Investigation (CCI) inpatient unit. Subjects will also complete at-home procedures, including an at-home PSG procedure. Subjects may log meals before inpatient admission and for up to 7 days after discharge with the app MealLogger™.

Follow-up Phase (4-12 weeks or until symptoms resolve)

- Follow-up phone call from the study coordinator 4 weeks after the final study visit and every 4 weeks thereafter to confirm resumption of menses and cessation of hot flashes (if they occurred).
- Study staff will also collect food and appetite measures that were recorded by subjects the end of Sleep Block 2
- Subjects who do not have resumption of menses or who continue to have hot flashes 4 months after receiving the leuprolide injection (3 months after final visit) will be referred to their routine medical provider for evaluation.
- A study summary letter will be sent to subjects once the final follow-up phone call has occurred. If there are any abnormal laboratory results listed in the letter that have not yet been discussed with the subject, a study clinician will call the subject to discuss prior to sending the letter.

Detailed Description of Sleep Blocks

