metabolic and stress markers will be collected during each visit. Blood samples will be collected repeatedly up to every 30 minutes during each visit. Blood will be drawn without interrupting sleep using an approximately 72" long IV line from outside the room and a blood-sparing technique to minimize blood loss. If issues with the IV occur, then select samples, up to 2 per wake episode may be drawn via venipuncture. Core Body Temperature will be measured with an oral thermometer. Hunger will be measured under both eucaloric and ad lib dietary conditions by administering Hunger Visual Analog Scales. On the day of admission, reproductive hormone levels will be tested, a urine pregnancy test will be performed, and morphometric measures will be gathered. During the inpatient stay, subjects will complete various questionnaires and tasks (e.g. Food Preference Questions, the Dutch Eating Behavior Scale, the Positive and Negative Affect Scale, hot flash diaries, reward seeking behavior, PSQI, ISI, PHQ-8). After waking, subjects may complete the post-sleep questionnaire and the CCI IPM Exit Questionnaire, which are regularly administered by CCI inpatient unit staff. Subjects may also complete neurobehavioral testing administered automatically by the computers on the CCI inpatient unit. Throughout the inpatient portions of the study urine voids may be scheduled to be collected approximately every 3 hours when the subject is awake. Unscheduled urine voids during the day or overnight may also be collected. For each void, the urine volume will be measured, and aliquots may be saved for later hormonal, metabolite, or electrolyte analysis of analytes that may be affected by sleep fragmentation and/or changes in hormonal status. Urine samples will be collected and stored per standard techniques. Skin conductance may be measured using the Biolog skin conductance monitor. During the 4 days prior to admission, subjects will receive several days of eucaloric meals from the CCI Nutrition Service, and ad lib breakfast will take place at BWH in order to measure food intake. Subjects will be instructed to standardize their sleep patterns during the 4 days at home, and up to a week beforehand, to extend the standardized routine.

- **Undisturbed procedures only:** Bedtime and wake-up time will be fixed to an 8-hour standardized TST.

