- Subject will be awakened during the night through auditory stimulus broadcast manually by sleep technicians throughout the night to achieve the target number of awakenings and minutes of Wake After Sleep Onset (WASO) (36 awakenings, 62 minutes WASO). Time In Bed (TIB) will be extended to maintain the 8-hour Total Sleep Time (TST). Auditory tones will be between 2- and 30-seconds duration, beginning at 60 dB and increased to a maximum of 1100db if an EEG awakening is not elicited. Once awake, subjects will be required to stay awake for up to 2 minutes. Subjects will not be permitted to get out of bed or eat in the middle of the night.
- Subjects will be able to order meals and snacks off a provided menu. There will be no dietary restrictions.

Nurses and technicians will be present 24 hours a day, so participants will have frequent social interactions in this controlled setting. Medical and psychologist/psychiatrist evaluation and treatment is available at all times.

Table of Procedures – Study overview

Table of Procedures - All Visits (revised 6/26/2020)						
Study Phase		Pre-Treatment				Post-treatment
Visit Type	Phone/Pre-screen	Screening Visit 1a	Screening Visit 1b	Sleep Block 1	GnRH-a Injection 1	Sleep Block 2
Time from Medication	remote	remote	in-person	in-person	in-person	in-person
General					0	1 week
	Informed Consent	x	x			
	Medical and Psychiatric Interview		x			
	Sleep Interview		x			
	Vitals, exam, & Morphometric measures			x	x	x
	Screening Labs			x		
	Questionnaires (via REDCap survey link)			x		
	Study Medication Administered					x
DXA	DXA Scan				x	
Blood tests	Adipokines				x	x
	Reproductive Hormones			x	x	x
	Metabolic Markers			x	x	x
	Stress			x	x	x
	Monitored Diet				x	x
Sleep Lab Assessments	Food intake/caloric consumption				x	x
	Hunger and Mood Ratings				x	x
	Energy Expenditure				x	x
	Polysomnography				x	x
	Skin Conductance					x
	Body Temperature				x	x
	Reward Behaviors				x	x
	Hot Flash Diaries				x	x
Eligibility Assessments	Sleep diaries				x	x
	Actigraphy Watch				x	x
	Berlin Questionnaire	x				
	PSQI	x			x	x
	ISI	x			x	x
	PHQ-8		x		x	x
	Urine Pregnancy Test				x	x
	PHQ-2	x				
	AE Monitoring		x	x	x	x

Study Endpoints

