Metabolic endpoints are: 1) fasting morning levels of leptin (primary) adipokines, ghrelin (total, acetylated) (secondary), and 2) the circadian leptin profile (exploratory), calculated as area under curve (AUC) to detect whether the overall profile is lower, as seen in sleep restriction studies, and morning fasting AD levels. Behavioral endpoints are: 1) satiety (primary) and hunger (secondary) on a VAS scale, and 2) daily caloric intake during ad lib meals (exploratory). Analyses of each endpoint will be conducted in parallel as we seek to detect coherence among endpoints and focus on consistency across different outcomes in each hormonal and HF context.

For studies involving treatment or diagnosis, provide information about standard of care at Partners (e.g., BWH, MGH) and indicate how the study procedures differ from standard care. Provide information on available alternative treatments, procedures, or methods of diagnosis.

This study involves the administration of leuprolide to healthy individuals in order to better understand experimentally induced hot flashes. Subjects are healthy individuals who do not have any specific medical diagnosis. The DXA scan is not clinically indicated for women participating in the protocol. Alternative imaging studies are therefore not indicated.

Describe how risks to subjects are minimized, for example, by using procedures which are consistent with sound research design and which do not unnecessarily expose subjects to risk or by using procedures already being performed on the subject for diagnostic or treatment purposes.

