Once in the laboratory, the subject will be constantly supervised by laboratory personnel. The medical physician for the BWH Clinical And Translational Science Center/Center for Clinical Investigation (CCI) inpatient unit will also be available on-call to handle any medical emergency that might arise. The subject's vital signs (pulse rate, respiratory rate, systolic and diastolic blood pressure) will be checked at least once per day. An approximately 72" long intravenous line will be placed during each of the CCI inpatient unit admissions so that venous blood samples can be obtained using an IV line from outside the room without repeated venipuncture or sleep interruption related to the blood draw. If issues with the IV occur, then select samples, up to 2 per wake episode may be drawn via venipuncture. Prior to the insertion of the IV catheter, the skin around the insertion site will be washed with a Betadine solution followed by alcohol. An anti-bacterial ointment will be applied to the IV catheter insertion site prior to dressing the site. Hypoallergenic tape will be used on the IV dressing to minimize the development of contact dermatitis. The IV catheter insertion will be done while the subject is supine, and a staff member will remain in the suite with the subject for at least 10 minutes after the insertion to ensure that the subject does not feel light-headed or dizzy. Blood-sparing techniques will be used to minimize blood loss. The total amount of blood drawn will be up to 447.5 cc. Federal guidelines allow for up to 550 cc of venous blood per 2-month period in healthy non- pregnant adults. Anemic subjects will be excluded from participation and hemoglobin will be repeated at the completion of the study to confirm the absence of anemia. Oral ferrous sulfate supplementation and clinical follow up will be provided if anemia is present.

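### Hemoglobin is checked at screening and at study completion but not between the two sleep blocks, so a mild, silent fall after the first set of draws would be found only after the second

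*Protocol*

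**What the plan says.** Exclusion criterion 16 of the full study covers laboratory abnormalities, "including specifically a hemoglobin <12 g/dl (given multiple blood draws"), qualified by the investigator's judgment of medical relevance. The safety section says more plainly that anemic women are excluded. The blood count is taken at Screening Visit 1b, where "a blood draw will be taken for screening assays (e.g., CBC, glucose, insulin, HCG, TSH").

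After that, the text states one further check, in the section on ensuring subjects' safety: "hemoglobin will be repeated at the completion of the study to confirm the absence of anemia". Oral iron and clinical follow-up are offered if anemia is found. The venous sampling risk section lists anemia as a risk and gives a study maximum of 447.5 cc, against a cited federal limit of 550 cc per two months.

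Between screening and completion, the described blood tests include no blood count:

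- Leuprolide visit: "blood will be drawn to measure reproductive hormone levels", with a urine pregnancy test.
- Each inpatient admission: "On the day of admission, reproductive hormone levels will be tested, a urine pregnancy test will be performed, and morphometric measures will be gathered".
- Within each stay: fasting adipokines, and other "metabolic and stress markers will be collected during each visit".
- Table of Procedures: "Screening Labs" carries a single mark. The other blood rows are adipokines, reproductive hormones, metabolic markers and stress.

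**The concern.** The protocol treats hemoglobin as relevant to whether a woman can safely undergo this sampling, then does not look at it again until all the sampling is over. Sleep Block 1 is placed two weeks before the injection and Sleep Block 2 four weeks after it. At the second block the latest result is therefore about six weeks old or more, and it predates every Sleep Block 1 draw. If menses start before leuprolide is given, the protocol moves to the next cycle and the gap is longer.

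The participants are healthy volunteers with no direct benefit. What is at stake is the timing of a remedy that the protocol already promises: iron given after the second set of draws cannot help a woman before them.

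**Working it through.** **Step 1: do other safeguards fill the gap?** Vital signs are taken at least daily in the unit, adverse events are monitored at every visit, and both off-study lists include a significant medical problem. Each depends on symptoms, abnormal vital signs or a recognized problem. They could catch symptomatic anemia, but would not be expected to show a mild, silent fall. Neither off-study list gives a hemoglobin level.

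**Step 2: the stated volume.** The 447.5 cc cannot be rebuilt, because the documents give no volume per sample, number of samples or split by block. Against the cited limit, 447.5 / 550 = 81.4%, which leaves 550 − 447.5 = 102.5 cc.

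**Step 3: how large could a fall be before Sleep Block 2?**

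From the protocol: the 447.5 cc maximum, the 12 g/dl entry value, and the minimum weight of 110 lb (49.9 kg).

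Assumed, because the documents do not say:

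- 40% to 60% of the maximum is drawn by the end of Sleep Block 1
- blood volume is 60 to 70 mL/kg
- the upper weight for illustration is 70 kg
- none to half of the loss is replaced before Sleep Block 2

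Fraction lost: f = volume drawn × (1 − share replaced) / (kg × mL/kg). The screening hemoglobin that would fall to exactly 12 is 12 / (1 − f).

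With a 50% split (0.5 × 447.5 = 223.75 cc), the results in g/dl are:

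| Weight and blood volume | None replaced | Half replaced |
|---|---|---|
| 49.9 kg × 60 mL/kg = 2,994 mL | 12.97 | 12.47 |
| 49.9 kg × 70 mL/kg = 3,493 mL | 12.82 | 12.40 |
| 70 kg × 60 mL/kg = 4,200 mL | 12.68 | 12.33 |
| 70 kg × 70 mL/kg = 4,900 mL | 12.57 | 12.28 |

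First cell: f = 223.75 / 2,994 = 0.0747, and 12 / 0.9253 = 12.97. With half replaced, the margin above 12 is 0.28 to 0.47, or about 0.3 to 0.5 g/dl.

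Extremes of the full range:

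- Lowest (40% split, 179 cc; 70 kg; 70 mL/kg; half replaced): f = 89.5 / 4,900 = 0.0183, giving 12.22.
- Highest (60% split, 268.5 cc; 49.9 kg; 60 mL/kg; none replaced): f = 268.5 / 2,994 = 0.0897, giving 13.18.

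The full margin is thus about 0.2 to 1.2 g/dl, and the top needs all four extremes together.

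**Step 4: sensitivity.** If only 80% of the maximum is drawn (358 cc), the full range is 12.18 to 12.93, and the 50% split with half replaced gives 12.22 to 12.37. A model in which each draw dilutes the blood that remains, 12 × exp(f), lowers the top of the full range from 13.18 to 13.13. Neither changes the conclusion.

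**The case against.** The strongest reply is that sampling anemia is already managed. There is a hemoglobin exclusion, a minimum weight set with the sampling plan in mind, a blood-sparing technique, a total below the cited limit, monitoring for symptoms, a closing hemoglobin, and iron. What remains is a mild fall found and treated at the end rather than in the middle, and the documents point to no specific clinical harm from that delay. This stands, and it is why the point is minor.

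The absence also rests on incomplete material. The weight criterion refers to a Section 1c for the sampling plan, and the risk section refers to a DSMG form; neither is available to check. The procedures table is damaged in extraction, so its single mark is weak evidence. The narrative supports the same reading without the table, but an interim check described elsewhere cannot be ruled out.

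Three stronger readings are tempting, and the documents do not support them:

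- **A reader might infer that 12 g/dl must still hold at Sleep Block 2.** It is a screening criterion, qualified by investigator judgment and set in anticipation of the draws. No text makes it a running limit, so a value below 12 at Sleep Block 2 would breach nothing.
- **A reader might want a count of affected women.** The documents give no hemoglobin distribution, so any count would be invented.
- **A reader might infer that the protocol form requires a hemoglobin stopping level.** It asks for objective removal criteria in general, not one for each laboratory value. A fixed rule to cut Sleep Block 2 sampling below a threshold would also be debatable, because it would lose within-woman pairs selectively in women with lower hemoglobin.

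**Conclusion.** The gap is real but small. On the text available, hemoglobin is measured before the first draws and after the last, and nothing scheduled between them would show a silent fall. A woman who enters near 12 g/dl could plausibly start Sleep Block 2 somewhat below it. The margin is about 0.3 to 0.5 g/dl with a 50% split and half replaced, and 0.2 to 1.2 g/dl over the full assumed range. These figures depend on the assumed split, blood volume, weight and replacement, and are illustrative only. No volume limit or protocol rule is breached. The point deserves action because the remedy is nearly free and brings forward care that the protocol already offers.

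**What to change.** Add a hemoglobin to the blood already drawn at the leuprolide visit, and enter it in the procedures table. If the result is below 12 g/dl, a study clinician reviews it before Sleep Block 2, offers the oral iron and follow-up already provided for, and decides whether serial sampling in Sleep Block 2 should be reduced. The fasting samples for the primary leptin endpoint are kept in any case. Here 12 g/dl prompts a review; it is not a removal limit. Record any iron use and any reduction in sampling. The visit falls about four weeks before Sleep Block 2, which leaves time to act.

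The cost is about 40 tests on blood already being drawn, plus a few lines of protocol text. There is an analytic cost in a few women. Iron begun between the blocks coincides with the Sleep Block 1 versus 2 contrasts used for Aims 2 and 3, and recording it does not remove that difference. Reduced sampling would lose some exploratory serial data, chiefly "the circadian leptin profile (exploratory"), and the within-woman pairs that depend on them.

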Document Title: Statistical Analysis Plan

Protocol Title: Menopausal Sleep Fragmentation: Impact on Body Fat Gain Biomarkers in Women

Protocol #: MGB Human Research Committee #2016P002821

NCT: 03047330

Document date: January 3, 2024

Biostatistical Analysis

Analysis approach: Metabolic endpoints are: 1) fasting morning levels of leptin (primary), adipokines, ghrelin (secondary), and 2) the circadian leptin profile (exploratory), calculated as area under curve (AUC) to detect whether the overall profile is lower, as seen in sleep restriction studies,⁵³ and morning fasting AD levels. Behavioral endpoints are: 1) satiety (primary) and hunger (secondary) on a VAS scale, and 2) daily caloric intake during ad lib meals (exploratory). Analyses of each endpoint will be conducted in parallel as we seek to detect coherence among endpoints and focus on consistency across different outcomes in each hormonal and HF context.

Our experimental design, methodology, and analytic approach are robust and unbiased. While only women will be enrolled, analyses and interpretation of results will take into consideration age and other relevant biological variables. Key covariates will be measured and included as potential predictors in multivariate analyses, including specific *a priori* examination for age, race, BMI, SES, and stressful events to reduce unexplained variability in the outcomes.¹⁴¹ Importantly, within-subject analyses using each woman as her own control and expected low attrition based on our prior experience with similar protocols will minimize potential bias.

To address **Aim 1** (*impact of menopause-related sleep fragmentation on metabolic and behavioral biomarkers of body fat gain*), the mean levels in each endpoint in response to experimentally fragmented sleep (**Hypothesis 1a & 1b**) will be examined using repeated-measures generalized linear mixed-model regression. Models will incorporate the 2 SB contrasts addressing **Hypothesis 1a and 1b** to simultaneously compare the impact of sleep fragmentation in the HF-free, estrogenized environment (**SB_{SF1} vs. SB_{UD1}**), and hypo-E2 environment with stable HF levels (**SB_{SF2} vs. SB_{UD2}**); exploratory analyses will adjust for HF, either categorized (e.g., any versus none) or number of HF. If there is an omnibus effect of experimental sleep fragmentation, we will conduct post-hoc analyses on each SB contrast to explore whether the impact of experimental sleep fragmentation is consistent across hormonal and HF contexts. To address **Hypothesis 1c**, mean levels in outcomes will be contrasted **SP_{UD3} vs. SP_{UD1}** to assess the impact of sleep disruption related to HF in the environment without experimental sleep fragmentation, comparing those developing HF (expected N=26) with those who do not develop HF; analyses will adjust for initial E2 level.

Aim 2 (*impact of HF on metabolic and behavioral biomarkers of body fat gain*) will be examined using a repeated-measures generalized linear mixed-model regression analysis to determine the effect of HF on mean levels of in metabolic and behavioral biomarkers. The regression will include SB contrasts that assess the impact of HF in the presence (**SB_{SF2} vs. SB_{SF1}**) and absence (**SB_{UD2} vs. SB_{UD1}**) of experimental sleep fragmentation. If an omnibus effect of HF is observed, post-hoc analyses will be conducted on each SB contrast to explore whether the impact of HF is consistent across sleep fragmentation contexts. Additional analyses will substitute objectively measured HF or night-time only HF.

To address **Aim 3** (*impact of estradiol withdrawal on metabolic and behavioral biomarkers of body fat gain*), the mean levels in each endpoint in response to estradiol withdrawal (**Hypothesis 3**) will be examined using repeated-measures generalized linear mixed-model regression. Models will incorporate the 2 estrogenized and hypo-E2 contrasts addressing simultaneously the impact of estradiol withdrawal in the unfragmented and fragmented sleep states. If there is an omnibus effect of estradiol withdrawal, we will conduct post-hoc analyses on each sleep state contrast to explore whether the impact of estradiol withdrawal is consistent across both sleep states. Exploratory analysis will include adjusting for HF – either categorical (yes/no or

none/infrequent/frequent) or continuous – and sleep HF-related disruption in the hypo-E2 state (second SB).

Exploratory Hypothesis #1 analyses will involve a repeated-measures generalized linear mixed-model regression similar to those proposed for the **Hypothesis 1a** analysis using the RQ as an indirect measure of resting EE as the dependent measure, and the same post-hoc paired contrasts and interaction terms for randomization order. **Exploratory Hypothesis #2** analyses will involve addition of interaction terms (between total body fat or visceral adiposity with sleep fragmentation, HF, or E2 withdrawal) to models described for **Aims 1–3**, to test for effect modification on each metabolic or behavioral endpoint. These analyses are by necessity exploratory in nature given the sample size of this complex experimental study. **Exploratory Hypothesis #3** will involve an omnibus repeated-measures regression model encompassing all 6 contrasts described in **Aims 1–3** with the PANAS Negative Affect scale score as the primary predictor and adjustment for fragmented versus undisturbed sleep given an expected association between sleep fragmentation and affect. Post-hoc analyses using paired t-tests on each SB contrast will be conducted to explore the potential variability of the impact of negative affect on each metabolic and behavioral biomarker across the sleep fragmentation, HF, and hormonal contexts. Psychological and cognitive factors driving eating behaviors on the DEBQ will also be explored.

Sample size: Forty subjects will complete all study procedures. Sample size calculations are based on pilot data correlations between the change in the number of EEG arousals and change in leptin levels from before to after receiving GnRHa. The observed Pearson and Spearman correlations are $r=-0.44$ and $r_s=-0.36$. The detectable correlation is $r=-0.43$ for a sample size of 40 and $r=-0.52$ for the subgroup analysis ($n=26$) in **Hypothesis 1c** ($\alpha=0.05$, 80% power). Because it takes 3 months (screening/menstrual tracking plus 2 months of active procedures) for each subject to complete the study and data analysis time is required after all procedures are completed, accrual is expected to be achieved in the first 39–42 months of the Award. The expected accrual rate of 1.1 subjects per month is therefore similar to that which [REDACTED] achieved in prior healthy volunteer studies with a similar number of in-lab nights. This rate is lower than the 1.7/month that [name] achieved with healthy volunteers to leuprolide studies but with less intensive procedures. To ensure that accrual proceeds as planned, we will advertise widely using postcards we have used to enroll 2.4 women/month to menopause studies and which colleagues used to enroll 2.2 healthy volunteers/month to a study with fewer nights in the sleep lab.¹⁴² Based on previous experience, we expect to consent up to 130 subjects in order to have 40 study completers, given that up to 10 women may not be eligible after completing screening procedures and an additional 8 women may decline to receive leuprolide after completing SB#1, and because some women will participate in pilot procedures only.
